*Hypothesis #3d:* An additional exploratory subaim will seek to identify other maternal physiologic and/or fetal neurobehavioral markers that may predict NAS severity.

*Aim #4:* Will evaluate the longitudinal neurobehavioral developmental profile of B+N exposed infants up to 1 month of age. Infant neurobehavioral development will be compared to a matched cohort of methadone exposed and a historical cohort of buprenorphine only exposed infants.

*Hypothesis#4a:* B+N-exposed infants will evidence mild neurobehavioral alterations in the first month.

*Hypothesis #4b:* B+N-exposed, as compared to methadone-exposed infants will exhibit less severe neurobehavioral alterations.

*Hypothesis #4c:* The neurobehavioral functioning of the B+N and buprenorphine-only exposed infants will be similar.

*Aim #5:* Will evaluate concentrations of B+N in breast milk, maternal and infant plasma among breastfeeding women maintained on B+N.

*Hypothesis #5a-c:* B+N concentrations in a) maternal plasma, b) breast milk c) infant plasma will be low

*Hypothesis #5d:* B+N concentrations in breast milk, maternal plasma and infant plasma will be related to maternal dose of B+N.

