**Infants:** Infants will be evaluated through one month of age using a standardized neurobehavioral evaluation of high risk, especially substance exposed infants, the NICU Network Neurobehavioral Scale (NNNS; Lester, 2001). Evaluation of infant neurobehaviors can inform care providers (pediatricians, neonatologists, nurses, occupational / physical therapists, etc.) and parents regarding optimal care practices for this group. The NNNS is a comprehensive assessment of neurologic integrity and behavioral functioning, including withdrawal and signs of stress. Descriptive statistics for this scale have been provided from a prospective, large longitudinal study (Lester, 2002). The 13 NNNS summary scores (habituation, attention, handling, quality of movement, regulation, non-optimal reflexes, asymmetric reflexes, stress/abstinence, arousal, hypertonia, hypotonia, excitability and lethargy) have been normatively described for both substance exposed and non-exposed infants (Tronick, 2004). We have previously described the NNNS profile for methadone-exposed infants (Velez, 2009). Assessments will be performed by trained, certified investigators on days 3, 14 and 30 of life in the hospital or in a quiet lab adjacent to the infant's hospital room.

**Breastmilk: Maternal samples:** Subjects will provide plasma and breast milk at times of peak maternal medication levels (i.e. 2 – 2 ½ hours after maternal dose of B+N) on days 2, 3, 4, 14 and 30 post-partum.

**Infant samples:** Infant plasma will be obtained on day 14 coincident with a heel stick for routine pediatric care (i.e. PKU test) when feasible. NAS scores will be abstracted per the parent protocol.

**Analysis of breast milk and plasma samples:** Plasma and breast milk samples will be analyzed by Sam Houston State University in Huntsville, Texas. These investigators have extensive analytical experience with gas chromatography-mass spectrometry (GCMS) and liquid chromatography tandem mass spectrometry (LCMSMS) for many drugs of abuse, their metabolites and illicit pharmacotherapies. This plasma method investigates buprenorphine and norbuprenorphine concentrations as well as the glucuronide metabolites. New analytical methods will be developed for B+N and metabolites in breast milk based on the analysis of these analytes in multiple matrices.

b. Study duration and number of study visits required of research participants.

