## 5. Inclusion/Exclusion Criteria

Fetal, Neonatal and Infant protocol: *Inclusion criteria:* 1. Current opioid use disorder (OUD) as defined by DSM 5 criteria 2.18-44 years of age with singleton pregnancies, generally uncomplicated by conditions that jeopardize pregnancy outcome 3. Gestation less than 34 weeks

**Exclusion criteria:** 1. Complications of pregnancy, including gestational diabetes, polyhydramnios, hypertension, placenta previa or significant risk of preterm delivery; 2. Evidence of fetal malformation detected by prenatal ultrasound; 3. Significant general maternal health problems that can affect fetal functioning, including Type I or gestational diabetes, alterations in thyroid functioning, HIV infection or hypertension; 4 Significant maternal psychopathology that would preclude informed consent, such as unstable schizophrenia; 5. Alcohol use disorder per DSM 5 criteria; 6. Significant benzodiazepine use which would portend seizure activity during the induction period. This will be determined for all women reporting benzodiazepine use at the time of program intake by the project psychiatrist(s). 6. For the B+N group: Women stable on methadone maintenance (defined as more than 3 consecutive days of dosing); 7. For the B+N group: Women coming to treatment reporting “street” methadone use (for more than 3 consecutive days); 8. Women planning for adoption of their infant.

**Breastmilk protocol:** 10 B+N exposed infants and their mothers from the fetal study who meet criteria for breastfeeding (i.e. illicit drug use/licit drug misuse abstinence in the last 90 days prior to delivery or counselor endorsement of breastfeeding in the case of abstinence 30-90 days prior to delivery, HIV negative status, no concurrent prescription medication use that is contraindicated in lactation, and legal custody of their infant at delivery) will be enrolled.

**Inclusion criteria:** 1. B+N maintained mother, enrolled in parent study. 2. Free of illicit drug use and licit drug misuse after 36 weeks gestation or 30-90 days prior to delivery by standardized urine toxicology drug screening and drug treatment compliant. 3. Delivery at 37 weeks or later determined by second trimester ultrasound which is standard of care at the facility of recruitment.

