*Breastmilk study:* Basic descriptive statistics (mean, standard deviation, range) will be used to report concentrations of B+N in breast milk of lactating women on days 2-4, 14 and 30. Additional considerations for associations between maternal dose, maternal plasma and breast milk concentrations will be examined using linear regression. Descriptive statistics will be used to report plasma concentrations of B+N in breastfeeding infants and linear regression to evaluate potential associations between infant B+N plasma concentrations and maternal B+N dose. Although potentially underpowered, we will also fit linear regression models for associations between maternal dose, maternal plasma concentrations and breast milk concentrations with maternal dose as the main predictor. Although limited power exists for longitudinal models in this study due to small subject numbers, we will fit mixed effects models to examine changes over time in breast milk B+N concentrations for each sampling time. The analyses proposed here are not meant to be exhaustive and cannot be due to space limitations. However, they illustrate our approach for examining the relations among the complex set of independent, dependent, and confounding variables collected in this proposal.

*Computation of Power:* Sample size estimates for each study were premised with a power of .8, alpha =.05, and large effect sizes as observed in our prior studies (Jansson, 2005, 2007a), which were conducted with a similar experimental design. Based on a conservative estimate of 50% non-completion, the total number of participants to be enrolled will be 160. In comparison samples, we will have 40 for buprenorphine, and 40 for methadone. Using available pilot data, for hypothesis 1, we would have 80% power to detect a mean difference of 4.23 (SD 6.68) in peak/trough fetal heart rate. For the mixed effects models, via simulation using pilot data, we would be powered to detect a trajectory difference of .35 per week between groups. For hypothesis 2, we would have 80% power to detect a mean difference of 4.12 (SD 6.49) in peak fetal heart rate. For the mixed effects models, via simulation, we would be powered to detect a trajectory difference of .32 per week between BN and buprenorphine.

For hypothesis 3, we would have 80% power to detect a mean effect size of ..63 for difference in NAS severity between groups

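### The breast-milk regressions on maternal dose and plasma do not say how five repeated samples per woman are handled; if the samples are pooled, standard errors will be too small

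*Combined protocol and SAP*

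**What the plan says.** The breast-milk substudy is to enrol "10 B+N exposed infants and their mothers from the fetal study" (section 5, Breastmilk protocol). Mothers give plasma and milk at peak medication level "on days 2, 3, 4, 14 and 30 post-partum" (section 4, Postnatal protocol). For the infant, "Infant plasma will be obtained on day 14 coincident with a heel stick for routine pediatric care", when feasible, so there is at most one value per infant.

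Hypothesis 5d in section 2 is that "B+N concentrations in breast milk, maternal plasma and infant plasma will be related to maternal dose of B+N".

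The Breastmilk study paragraph of section 7b assigns the associations to linear regression twice. The first mention is "Additional considerations for associations between maternal dose, maternal plasma and breast milk concentrations will be examined using linear regression". The second, introduced with a warning about power, makes dose the chief explanatory variable: "we will also fit linear regression models for associations between maternal dose, maternal plasma concentrations and breast milk concentrations with maternal dose as the main" (the quote stops one word short of the end of the sentence). Neither mention gives a random effect, a clustering adjustment, a restriction to one day or a summary per woman. For time trends in milk, the same paragraph says "we will fit mixed effects models to examine changes over time in breast milk B+N concentrations for each sampling time".

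**The concern.** Five samples from one woman are unlikely to be independent: they share her metabolism, her milk composition and, largely, her dose. The paragraph recognises the repeated structure for time trends but is silent on it for the associations. The plan is more specific elsewhere. Aims 1 and 2 use mixed models with random intercepts, and the methadone comparison in hypothesis 2b is confined to the 36-week data.

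Because the unit of analysis is open, an analyst could follow the text to the letter and run ordinary regression on all samples. Hypothesis 5d could then be supported by intervals that are too narrow. The plan's warning about low power does not cover this. Low power means missed associations, whereas ignored clustering produces false ones.

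**Working it through.** **Inputs from the documents.** There are 10 women and 5 sampling days, so at most 10 × 5 = 50 milk and plasma pairs. Alpha is 0.05; sidedness is not stated and is taken as two-sided. The plan gives no sample size, power or standard error for the breast-milk study, so there is no figure to reproduce.

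**Assumptions.** The documents give no within-woman correlation (ICC), so it is ranged. Dose is first taken as constant within a woman, with all five samples obtained.

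**Step 1. Dose as predictor, samples pooled.** For a predictor constant within a woman:

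- Design effect = 1 + (5 − 1) × ICC
- Standard error factor = √(design effect)
- Effective sample size = 50 / (design effect)

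Type I error comes from simulating pooled least squares on 10 women × 5 samples with no true association. Runs of 5,000 to 40,000 replicates agree to within about 1.5 percentage points.

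| ICC (assumed) | Design effect | SE factor | Effective n | Type I error at nominal 5% |
|---|---|---|---|---|
| 0.1 | 1.4 | 1.18 | 35.7 | about 10% |
| 0.3 | 2.2 | 1.48 | 22.7 | 19% to 20% |
| 0.5 | 3.0 | 1.73 | 16.7 | 28% to 29% |
| 0.8 | 4.2 | 2.05 | 11.9 | 38% |
| 0.9 | 4.6 | 2.14 | 10.9 | 41% |

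The simulated standard error ratios are slightly larger than the formula gives (1.51 at ICC 0.3, 1.81 at 0.5, 2.32 at 0.9), so the formula does not exaggerate.

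**Step 2. Milk on maternal plasma, samples pooled.** Plasma varies within a woman, so the approximate design effect is 1 + 4 × ICC(milk) × ICC(plasma). With ICC(milk) = 0.5:

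| ICC of plasma (assumed) | Design effect | SE factor | Simulated SE ratio | Simulated type I error |
|---|---|---|---|---|
| 0.9 | 1 + 4 × 0.45 = 2.8 | 1.67 | 1.69 | 25% |
| 0.5 | 1 + 4 × 0.25 = 2.0 | 1.41 | 1.39 | 16% |
| 0.3 | 1 + 4 × 0.15 = 1.6 | 1.26 | 1.25 | 12% |
| 0 | 1.0 | 1.00 | 1.00 | 5% |

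**Step 3. Readings that avoid the problem.** Regression on woman means (10 − 2 = 8 degrees of freedom) or on a single day gave simulated type I error of 4.7% to 5.2% at every ICC tried. The reference distribution matters with 10 women: a normal reference in place of t on 8 degrees of freedom still rejects in 8% to 9% of runs.

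**Step 4. Infant plasma on maternal dose.** With one day-14 sample per infant there is no repetition, and the issue does not arise.

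**The case against.** A reader might infer that the plan commits to treating 50 samples as independent, so that its standard errors are certainly too small. The documents do not support that. Nothing in section 7b says the samples are pooled. The paragraph separates the linear regressions from the longitudinal models and reports descriptive results by day. That fits regressions run by day or on one value per woman, and both would be valid. The authors plainly know mixed models. This stands, and it makes the finding conditional.

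A reader might also infer that the whole of hypothesis 5d is exposed. It is not. The hypothesis relates milk, maternal plasma and infant plasma to dose. The infant part is unaffected, and milk against plasma is a separate association named only in section 7b.

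Nor do the documents support the inference that feeding advice would turn on this. No decision rule or power calculation attaches to hypothesis 5d, the substudy has 10 pairs, and the descriptive results for hypotheses 5a to 5c do not depend on these regressions.

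The sizes in Step 1 also need a stable dose and complete sampling. The documents do not say that dose is constant over days 2 to 30, and the procedures allow adjustment. Within-woman variation in dose would reduce the inflation.

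The plan's statement that its list of analyses is not exhaustive is a weaker defence. It excuses analyses left out, but does not settle how a named one is to be done.

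**Conclusion.** The plan names linear regression, without a woman-level term or a unit of analysis, for associations measured up to five times in each of 10 women. That gap is certain; the error that follows is conditional on pooling.

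Under pooling with a stable dose, complete samples and an assumed ICC of 0.3 to 0.8, the standard error for dose is about 1.5 to 2.0 times too small and type I error is about 20% to 38%. Milk on plasma is affected less, and not at all if plasma does not cluster by woman. Severity is low: this is a small, largely descriptive substudy, and the remedy is nearly free.

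**What to change.** Replace the two regression statements in section 7b with a specification along these lines:

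- **Hypothesis 5d, maternal outcomes.** Fit two separate models, milk on dose and maternal plasma on dose. Each has a random intercept per woman, sampling day as a fixed effect and small-sample degrees of freedom (for example Kenward-Roger). Alternatively, regress one summary per woman (n = 10). With complete data and a stable dose, the two routes give the same test of dose.
- **Milk on plasma.** Fit this as its own mixed model. Do not add plasma to the milk-on-dose model. Plasma plausibly lies between dose and milk and is itself an outcome under hypothesis 5d, so adjusting for it would change the question.
- **Infant plasma on dose.** Keep simple linear regression.

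Regressions by day would also be valid, but they split the data into five sets of at most 10 women and make less use of it than the mixed model.

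The cost is a sentence or two in the SAP, with no new samples, visits or participants. The price is wider intervals than pooled regression would give.

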## 8. Risks

a. Medical risks, listing all procedures, their major and minor risks and expected frequency.

There is a growing body of literature to support the relative safety and efficacy of buprenorphine use during pregnancy (Jones, 2010; Fischer, 2005; Jansson, 2010; Kakko, 2008, Lejeune, 2006), and the use of naltrexone, a compound similar to naloxone, produces no untoward effects when used in pregnancy in general to the mother or infant. One study evaluating fetal effects of maternal naloxone treatment at term found mild increases in fetal heart rate accelerations, fetal breathing and fetal movements (Arduini, 1986) all signs of fetal well-being. More recently, several observational studies have reported the relatively good outcomes in buprenorphine-naloxone exposed infants (Debelek, 2013, Dooley, 2016, Weigand, 2015, Gawronski, 2014) However, any medication used during pregnancy can present some risk to the mother and/or fetus. Risk to the neonate includes Neonatal Abstinence Syndrome (NAS), which occurs with less severity in buprenorphine, as compared to methadone exposed infants (Jones, 2010) however, there are no additional risks to the acquisition of NAS data. There are no known risks to fetal monitoring procedures for mothers or fetuses. There is no risk to the acquisition of breathalyzer testing, CO testing, or urine toxicology testing to subjects. Subjects will have additional urine toxicology screenings that CAP patients. There are no known risks of the NNNS exam that will be administered to infants.

For Buprenorphine-naloxone in particular, side effects are:

More Common reactions: Constipation (14% ), Nausea (23% ), Vomiting (11% ), Xerostomia (5% or greater), Dizziness (16% ), Headache (36% ), Somnolence (14% ) Withdrawal syndrome (25%), pain (22%), Diaphoresis (14%)

Less Common reactions: Vasodilatation (9%) Vomiting (8%)

Serious Reactions, but rare (<1%): Syncope, Application site reaction, Anaphylaxis, Hypersensitivity reaction, Loss of consciousness, Respiratory depression, Respiratory distress, Respiratory failure, Drug withdrawal.

Further, plasma and breast milk samples might induce minor bleeding, discomfort and bruising.

**b. Steps taken to minimize the risks.**

There could be a potential risk of buprenorphine-naloxone induction for pregnant opioid dependent patients, which would involve some degree of opioid withdrawal and/or stress; effects of maternal opioid withdrawal on the fetus are not known. There might be some risk to the sobriety of a methadone maintained patient who would undergo withdrawal from methadone to accept B+N. Therefore, this protocol will enroll only methadone naïve subjects (3 or less days of “street” methadone intake or methadone dosing) to minimize this risk for the B+N cohort. Subjects will have additional urine specimens collected for urine toxicology screening during the period of study enrollment, however, these results will not be shared with CAP or other treatment program staff and therefore present no risk to the subject’s status in substance use disorder treatment.

**c. Plan for reporting unanticipated problems or study deviations.**

Any adverse events or serious adverse events will be reported to the IRB, the NIDA project officer, the FDA (via the holder of the IND for this study TBD) and to the study Data Safety Monitoring board.

**d. Legal risks such as the risks that would be associated with breach of confidentiality.**

There is some risk to subjects from breach of confidentiality of their status as drug dependent people. The study will take place within the Center for Addiction and Pregnancy, a drug treatment facility, where patient status is kept confidential in compliance with federal regulations. Study records will be stored by study staff in a de-identified database, and records will be kept in a locked filing cabinet within a locked room.

**e. Financial risks to the participants.**

None anticipated.

## **9. Benefits**

**a. Description of the probable benefits for the participant and for society.**

Subjects and their infants may benefit from participation by receiving B+N as opposed to methadone. Methadone treatment is the standard of care for opioid dependent pregnant women in the US and at CAP. There is a growing interest in the use of B+N during pregnancy due to the reduced incidence of severe NAS in infants. Infants may benefit from the NNNS examination, which may provide information regarding the infant’s neurobehavioral strengths and difficulties that may be beneficial to the caretaker.

Benefits to society are larger. It has been established that buprenorphine is an acceptable alternative to methadone for use during pregnancy, and its use may confer an advantage to both fetal and infant functioning. But there is no information on the combination drug B+N, and many women maintained on this medication with success are currently required to switch to an alternative preparation when they become pregnant due solely to a lack of evidence regarding effects on the fetus and infant. Specific hypotheses for this study are based on the premise that B+N maintenance during pregnancy will generate fewer adverse effects on offspring than methadone, and either the same degree or lesser deleterious effects as conferred by buprenorphine. Confirmation of hypotheses will directly benefit the care given to women with opioid use disorders who seek medication assisted treatment during pregnancy and to society, as adding naloxone to buprenorphine-only will reduce abuse liability and drug diversion, and likely increase drug effectiveness by allowing medication adherence throughout pregnancy to women vulnerable to relapse.

## **10. Payment and Remuneration**

- a. Detail compensation for participants including possible total compensation, proposed bonus, and any proposed reductions or penalties for not completing the protocol.

Pregnant women will be compensated \$25 per fetal testing day, for a maximum of \$100, which will be delivered at the completion of the final testing session in the form of a gift card for baby supplies. Mothers will receive a \$20 gift certificate for each study visit involving an infant assessment (days 3, 14 and 30) for a total of up to \$60. The total possible compensation for participation is \$160.

## **11. Costs**

- a. Detail costs of study procedure(s) or drug (s) or substance(s) to participants and identify who will pay for them.

Study medication and procedures will be provided at no cost to subjects. Should the study be funded by NIDA, study medications for CAP participants provided by the manufacturer (Indivior) per written agreement with the study PI. Medications received in other treatment programs will be provided by those treatment programs.
